SLE is a chronic inflammatory disease that has renal effect in about half of patients. Lupus nephritis is a major risk factor for morbidity and mortality in patients with SLE, and in spite of strong anti-inflammatory and immunosuppressive therapies still ends in CKD or ESRD. (5)

Based on this observation, we aim to determine the effect of SGLT2i treatment in patients with glomerulonephritis secondary to SLE who either is diabetic or non-diabetic.

Aim of the work

This study aims to assess SGT2i role in regression of ongoing kidney and cardiac diseases among lupus nephritis patient either diabetic or non-diabetic under different immunosuppressive therapy.

Patients and methods

Technical design:

Study sitting: .1

Nephrology and renal transplant unit at urology and nephrology center in Mansoura University.

It will include 100 patients with lupus nephritis, Diagnosis of glomerulonephritis was performed by renal biopsy, and all of the renal biopsies were carried out at urology and nephrology center.

Patients with an estimated glomerular filtration rate (eGFR) >30 ml/min/1.73m2 will be randomized into two groups

- Study group will receive SGLT2i inhibitor as add on drug or replace
 another drug according to patient clinical situation, Dapagliflozin 10
 mg and 25 mg will be used once daily with or without food.
 - Control group will be maintained on placebo. •

The primary endpoint will be sustained decline in eGFR ≥50%, ESKD, or kidney or cardiovascular death

We will follow up all patients for 12 months and compare their results.

2. Inclusion criteria:

- Patients aged more than 16 year. .1
- Willing to sign informed consent. .2
- Diagnosis of SLE according to EULAR/ACR classification .3 criteria.
 - Renal biopsy showed lupus nephritis. .4
- Patient with eGFR > 30 ml/min/1.73m2 by cockcroft-gault .5 equation.

3. Exclusion criteria:

- Patients with eGFR <30 ml/min per 1.73 m2. .1
 - Current pregnancy or lactation. .2
- Medical history of chronic disease (CLD, cancer, severe .3 respiratory distress, gastrointestinal tract lesions).
- Patients refusing to participate in the study or lost follow up. .4
- Evidence of urinary obstruction of difficulty in voiding at .5 screening.

- Patients who are receiving high dose diuretics or combined .6 ACEI, ARBS.
- Patients who have frequent hypotensive episode or SBP .7 <100 mmHg.

Operational design:

Study Protocol:

Patients included in the study will treated with dapaglifilozin
 initiated at a total daily dosage of 10 mg/kg per day.

Study design:

Type of the study: randomized controlled study.

The following data will be gathered and evaluated for all patients:

I-before intervention:

- Serum creatinine, Creatinine clearance. .1
- 24 hour urine protein, urine protein/creatinine ratio. .2
 - Urine analysis. .3
 - HBA1c. .4
 - HGB. .5
 - Uric acid and lipid profile. .6
 - Lupus serology. .7

II-after intervention: All patients will be evaluated monthly regarding:

- Serum creatinine, creatinine clearance. .1
- 24 hour proteinuria, protein/creatinine ratio. .2
- Fasting, random and postprandial glucose levels. .3
 - CNI trough level if used. .4
 - Urine analysis. .5
 - HGB level. .6
 - Uric acid, lipid profile. .7
 - Lupus serology. .8

Cardiovascular assessment: .9

ECCHO.

Atherosclerosis and vascular calcification incidence (NCCT model).

Regular measurement of blood pressure each visit.

Outcomes:

- Effect of dapagliflozin compared to placebo on eGFR. .1
- Effect of dapagliflozin compared to placebo on systolic/diastolic blood .2 pressure.
 - Effect of dapagliflozin compared to placebo on body weight. .3
- Safety of dapagliflozin vs. placebo the number of hypoglycemia .4 episodes between groups and serious adverse events.

Statistical Analysis:

Qualitative data were displayed in cross tabulations, and quantitative data were described in terms of arithmetic mean ± SD. Bivariate techniques were used for initial evaluation of contrasts. Thus, the chi-square and Fisher's exact tests were used for comparisons of frequencies of qualitative variables; the Mann-Whitney test and the unpaired t-test were used for comparisons of means of two quantitative variables. A p-value <0.05 was considered significant. Graft and patient survival rates were assessed using the Kaplan-Meier method. All analyses were carried out using the computer package SPSS for windows, release 16 SPSS Inc. Chicago, III, USA.

Administrative design •

Informed consent will be obtained from all subjects and the approval will be obtained from institutional review board (IRB) in Faculty of Medicine, Mansoura University. There is no funding.

Research question

The main research question is: Does use of SGLT2i will show superiority over conventional lines of treatment of lupus nephritis patient as regard efficacy and safety.

Rationale and justification

The rational of this study is that SGLT2i are now one of the common lines in regression of chronic kidney disease either is diabetic or not.

Large trials on this issue exclude patient with glomerulonephritis, so we will study its renal efficacy in patient with secondary glomerulonephritis to SLE to prove their efficacy and safety in this group of patients.

Objectives

The main objective of this study is to:

- To compare use of SGLT2i versus standard care in regression of chronic kidney disease in patient with LN.
 - To study the safety and efficacy of this drug group with use of immunosuppression and possible interaction.

Hypothesis

leading causes SLE is the one of the of secondary glomerulonephritis. Despite the use immunosuppressive and antiproteinuric drugs, a number of patients are at risk of progressing to end-stage kidney disease. Additional therapies to slow kidney function decline are highly desired. The DAPA-CKD trial demonstrated that the sodium glucose co-transporter 2 inhibitor dapagliflozin significantly reduced the risk of kidney failure and prolonged survival in participants with chronic kidney disease with and without type 2 diabetes. The DAPA-CKD population excluded patients with lupus nephritis, so we determined the long-term efficacy and safety of dapagliflozin on major

kidney and cardiovascular outcomes in these patients.

References

- James Matera, DO. SGLT2 Inhibitors and CKD in -1 2021. Consultant360. Published online May 25, 2021.
- Dan Xu, Owain Chandler, Cleo Wee, et al. Sodium--2
 Glucose Cotransporter-2 Inhibitor (SGLT2i) as a Primary
 Preventative Agent in the Healthy Individual: A Need of
 August 2021
- Hiddo J.L. Heerspink, Ph.D., Bergur V. Stefánsson, et-3al. Dapagliflozin in Patients with Chronic Kidney Disease.N Engl J Med 2020; 383:1436-1446.
- Kana N. Miyataa, Shao-Ling Zhanga John S.D. Chana-4. The Rationale and Evidence for SGLT2 Inhibitors as a-4Treatment for Nondiabetic Glomerular Disease.CJASN May 2017, 12 (5) 825-835.
- Salem Almaani, Alexa Meara and Brad H. -5 Rovin. Update on Lupus Nephritis Clin PharmacolTher 2007;81:228-34. 10.1038/sj.clpt.6100039.

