Statistical Analysis Plan

Document Control

Title: Statistical Analysis Plan for the Study of SGLT2 Inhibitors in Lupus Nephritis Patients

Protocol ID: [NCT05748925] Version: 1.0 Date: [11/3/2024] Principal Investigator: [[name]] Statistician: [[name]] Approval Signatures: Principal Investigator: [name] Statistician: [name]

Table of Contents

- 1. Introduction
- 2. Study Design
- 3. Study Objectives
- 4. Endpoints
- 5. Sample Size Justification
- 6. Statistical Methods
- 7. Handling of Missing Data
- 8. Interim Analysis
- 9. Safety Analysis
- 10. Data Quality and Management
- 11. Software
- 12. Appendices

1. Introduction

• **Purpose of the SAP**: This document outlines the statistical approach for analyzing data from the clinical trial studying the effects of SGLT2 inhibitors on renal, cardiovascular, and hematological outcomes in lupus nephritis patients.

2. Study Design

Design: Randomized, double-blind, placebo-controlled clinical trial.

Study Duration: Conducted from September 2022 to November 2023

Randomization: Patients were randomly assigned to either dapagliflozin (10 mg once daily) or placebo groups using computer-generated random tables in a 1:1 ratio stratified by age and gender.

Blinding: The study was double-blinded, and all trial staff and participants remained unaware of individual treatment assignments until study completion.

3. Study Objectives

Primary Objective: To evaluate the impact of SGLT2 inhibitors on renal, cardiovascular, and hematological parameters in lupus nephritis patients.

Secondary Objective: To explore changes in body weight, BMI, and other echocardiographic and iron profile parameters over 12 months.

4. Endpoints

Primary Endpoints

Renal Function: Serum creatinine, eGFR, and 24-hour urine protein

Cardiovascular Health: BNP levels and coronary calcification via NCCT

Hematological Parameters: Hemoglobin and erythropoietin levels

Hepcidin Level: Measured before and after intervention

Secondary Endpoints

Body Weight and BMI: Assessed at baseline and follow-up visits.

Echocardiographic Findings: Assessed pre- and post-intervention.

Iron Profile: Serum ferritin and TSAT

5. Sample Size Justification

Calculation: A sample size of 100 patients was targeted, accounting for potential dropouts, to provide sufficient power (80%) at a significance level of 0.05 to detect differences between the two groups.

6. Statistical Methods

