
General Considerations

Significance Level: A two-sided alpha level of 0.05 will be used for all primary analyses.

Analysis Populations:

Intent-to-Treat (ITT): All randomized patients will be analyzed according to their assigned group.

Per-Protocol (PP): Only patients completing the study without major protocol violations.

Primary Endpoint Analysis

Renal Outcomes: ANOVA for repeated measures for serum creatinine and eGFR if normally distributed, and the Friedman test for non-normally distributed data. Post-hoc tests using Bonferroni correction.

Cardiovascular Outcomes: Mann-Whitney U test for BNP levels and coronary calcification between groups.

Hematological Outcomes: Paired t-test for hemoglobin and erythropoietin levels if data is normally distributed; otherwise, Wilcoxon signed-rank test.

Secondary Endpoint Analysis

Body Weight and BMI: Compared over time using ANOVA for repeated measures.

Echocardiographic Parameters: Analyzed with paired t-tests, adjusted with Bonferroni correction.

Iron Profile: Analyzed pre- and post-intervention using ANOVA or Kruskal-Wallis for non-normally distributed variables.

Categorical Variables

Chi-Square Test: For between-group comparisons of categorical data (e.g., presence of diabetes, hypertension).

7. Handling of Missing Data

Imputation: Last observation carried forward (LOCF) for data missing at random; multiple imputation for extensive missing data.

Sensitivity Analysis: Conducted to evaluate the robustness of primary endpoint findings against different missing data assumptions.

8. Interim Analysis

Timing: An interim analysis is planned at the halfway point (6 months).

Stopping Rules: An O'Brien-Fleming approach will be applied to adjust the significance threshold for interim testing, allowing for an earlier stop for efficacy or safety concerns.

9. Safety Analysis

Adverse Events (AEs): Summarized by type, frequency, and severity. Fisher's exact test will be used to compare AE rates between groups.

Specific Safety Parameters: Monitoring for hypotension, electrolyte imbalances, and kidney function.

10. Data Quality and Management

Data Quality Measures: Includes data verification, regular audits, and query resolution.

Database Lock: Data will be locked and verified prior to the final analysis.

11. Software

Statistical Software: All analyses will be conducted using SPSS (Version 25).

12. Appendices

	Control group. (n= 41)	Study group. (n= 38)	P value

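### An objective asks about interaction with immunosuppression, but no outcome comparison uses regimen, diabetes or the stratification factors

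*Protocol*

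**What the plan says.** - **Protocol, Aim of the work:** the drug's role is to be assessed "among lupus nephritis patient either diabetic or non-diabetic under different immunosuppressive therapy".
- **Protocol, Objectives, second item:** "To study the safety and efficacy of this drug group with use of immunosuppression and possible interaction".
- **SAP section 2, Randomization:** allocation is "using computer-generated random tables in a 1:1 ratio stratified by age and gender".
- **SAP section 6, renal outcomes:** "ANOVA for repeated measures for serum creatinine and eGFR if normally distributed, and the Friedman test for non-normally distributed data". BNP and coronary calcification get a Mann-Whitney test. Haemoglobin and erythropoietin get paired tests.
- **SAP section 6, Categorical Variables:** a chi-square test, "For between-group comparisons of categorical data (e.g., presence of diabetes, hypertension". This is the only mention of diabetes among the SAP's methods. Immunosuppressive regimen is not mentioned there.
- **Protocol, Statistical Analysis:** two-group bivariate tests and Kaplan-Meier curves, with no covariates.
- **SAP section 12:** Tables 1 and 2 compare diabetes and regimen between arms at baseline, each with a stated p of 0.2. Tables 6 to 10 compare whole arms without adjustment.

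**The concern.** The second objective needs some analysis that relates the treatment comparison to the immunosuppression a patient receives, and none is specified. The aim also opens the population on diabetes and regimen, so the result will naturally be read as covering all of those patients, although no estimate by either factor will exist.

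There is a second gap. Age and gender were used to stratify allocation, but they are left out of every outcome comparison. An analysis that ignores its stratification factors usually loses some precision and does not match the design.

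At stake are an objective that ends without an answer, and a conclusion worded more broadly than its evidence.

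**Working it through.** **1. Coverage.** Going through SAP section 6 and the protocol's statistical section for any outcome comparison that uses each factor:

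| Factor | Role in the documents | Used in an outcome comparison? |
|---|---|---|
| Regimen | Aim and second objective | No |
| Diabetes | Aim | No (frequency comparison only) |
| Age, gender | Stratification factors | No |

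The one subgroup-type look, Figure 2 in the SAP appendix, is by baseline eGFR in the pooled cohort. CNI trough level is collected monthly where relevant, but no analysis of it is described.

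**2. Reproducing the stated balance p-values** (SAP Tables 1 and 2; control 41, study 38). Pearson chi-square for a 2×2 table is N(ad − bc)² / (product of the four margins).

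- Diabetes, 7/41 vs 11/38: 79 × (7×27 − 34×11)² / (41×38×18×61) = 1.58, p = 0.209. Stated: 0.2.
- Regimen, counts 27, 5, 2, 7, 0 vs 18, 4, 1, 14, 1 (sums 41 and 38): chi-square 5.47 on 4 df, p = 0.242. Stated: 0.2.

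Both stated figures reproduce.

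**3. Size of the descriptive differences** (study minus control).

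- Diabetes: 28.9% − 17.1% = 11.9 points before rounding (95% CI −6.6 to 30.3).
- Steroid + azathioprine: 14/38 − 7/41 = 36.8% − 17.1% = 19.8 points before rounding (0.6 to 38.9). Pearson p = 0.047, Fisher 0.073, Yates 0.083.
- Any MMF: (18+1)/38 − (27+2)/41 = 50.0% − 70.7% = −20.7 points. Pearson p = 0.059, Fisher 0.069.

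**4. Possible shift in the eGFR contrast.** Shift = difference in prevalence × prognostic effect of the factor. The documents give no prognostic effect, so 5 to 20 ml/min is assumed.

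- Diabetes: 0.119 × 5 = 0.6, up to 0.119 × 20 = 2.4 ml/min.
- Azathioprine: 0.198 × 5 = 1.0, up to 0.198 × 20 = 4.0 ml/min.

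**5. Precision at 12 months** (SAP Table 6: SD 44.5 control, 48 study). Pooled SD = √[(40×44.5² + 37×48²)/77] = 46.2. Half-width = SD × √(1/n₁ + 1/n₂) × t. The whole-sample SD is assumed to hold within subgroups.

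- All patients, 41 vs 38: 46.2 × 0.225 × 1.99 = 20.7 ml/min.
- Diabetics, 7 vs 11: 46.2 × 0.483 × 2.12 = 47.4 ml/min.
- MMF-containing, 29 vs 19: 46.2 × 0.295 × 2.01 = about 27 ml/min.
- No MMF, 12 vs 19: 46.2 × 0.369 × 2.05 = about 35 ml/min.

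**6. What an interaction test could detect** (two-sided 0.05, 80% power, normal approximation). Smallest detectable interaction = (1.96 + 0.84) × √(sum of 1/cell size), in SD units.

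- Diabetes (7, 34, 11, 27): 2.80 × 0.548 = 1.54 SD.
- Any MMF (29, 12, 19, 19): 2.80 × 0.472 = 1.32 SD.
- For comparison, the main effect: 2.80 × 0.225 = 0.63 SD.

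Power for an interaction as large as 0.63 SD is 21% for diabetes and 27% for MMF.

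**The case against.** **The aim's wording describes who is enrolled.** This stands. The main research question and first objective ask for one comparison in lupus nephritis, and the SAP's objectives name neither factor. A reader might infer that the protocol asks whether the effect differs by diabetes; no passage says so. For diabetes the point is therefore about how far the conclusion reaches.

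**Interaction may mean drug interaction.** The second objective allows that reading. It does not close the gap, because no analysis is specified under either reading.

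**Immunosuppression is not wholly absent from the SAP.** The appendix compares regimen and cyclophosphamide at baseline, and MMF intolerance and steroid increases during follow-up. The last two bear on safety, but they do not relate the treatment effect to regimen.

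**The arms are not shown to be confounded.** A reader might infer confounding, or failed randomisation, from the azathioprine p of 0.047. The documents do not support either. That category is one of five picked after seeing the data, its exact and continuity-corrected p-values exceed 0.05, and the overall regimen p is 0.24. The tables cover 79 of a targeted 100 patients, and the available text does not show whether the differences arose at allocation or through later losses.

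**Subgroup and interaction estimates will be weak.** True, as step 6 shows. This argues for exploratory labels and for restraint in the conclusion. It does not excuse leaving an objective unaddressed.

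**Diabetes might seem the better stratum than gender.** No continuation is described, so advice on strata has no use here.

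**Conclusion.** The gap between the second objective and the planned analyses is real and rests on the documents alone. As written, the plan leaves that objective unanswered and ignores the stratification factors in analysis. Its result applies to a mixed sample that is 61/79 (77%) non-diabetic.

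The between-arm differences in diabetes and regimen are compatible with chance. They may shift the eGFR contrast by roughly 0.6 to 4.0 ml/min under the assumed prognostic effects, which is small beside the overall half-width of about 21 ml/min.

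Separate claims are not supportable: the half-width in diabetics is about 47 ml/min if the whole-sample SD applies to them. The matter should be corrected, but it does not invalidate the trial.

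**What to change.** In SAP section 6, for the continuous endpoints:

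1. Add a between-arm regression or ANCOVA with baseline value, age and gender.
2. Add diabetes (yes/no) and MMF-based regimen (yes/no) in a sensitivity model.
3. Tabulate the arm difference with 95% CI by regimen and by diabetes status, with each interaction estimate.
4. Label all of these additions, including the adjusted contrast, post hoc and exploratory, because the SAP already tabulates results.
5. State that the conclusion applies to the mixed sample, and make no claim by diabetes status or regimen.

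If the models are declined, the minimum is item 5 plus a statement that the interaction part of the second objective was not analysed.

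**Cost:** the variables are already collected. Rank and paired tests take no covariates, so a model has to be added rather than a term or two. The subgroup intervals will be wide, and the conclusion becomes narrower than the aim's wording.

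### The protocol lets the SGLT2 inhibitor replace an unnamed background drug in the study group only; used as written, that is not a dapagliflozin-versus-placebo comparison and cannot be blinded

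*Protocol*

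**What the plan says.** The Technical design part of the protocol describes the two groups in consecutive bullets. For the active arm: "Study group will receive SGLT2i inhibitor as add on drug or replace", continuing on the next line "another drug according to patient clinical situation". For the other arm: "Control group will be maintained on placebo".

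The protocol's Study design line reads "Type of the study: randomized controlled study" and does not mention blinding. Its Outcomes list is framed as drug against placebo: "Effect of dapagliflozin compared to placebo on eGFR", the same for blood pressure ("Effect of dapagliflozin compared to placebo on systolic/diastolic blood"), and for safety "Safety of dapagliflozin vs. placebo the number of hypoglycemia" episodes. The Objectives name a different comparator: "To compare use of SGLT2i versus standard care in regression of chronic kidney disease in patient with LN". The Research question likewise asks about superiority over usual treatment.

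SAP section 2 describes a 1:1 double-blind comparison of dapagliflozin 10 mg once daily with placebo, in which neither staff nor participants knew assignments until the end. It does not mention replacement, either to keep it or to withdraw it. SAP section 6 defines an intention-to-treat (ITT) set by assigned group, and a per-protocol set that depends on major violations it does not define. Neither document says how changes in background drugs are to be handled.

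**The concern.** A placebo-controlled trial isolates a drug's effect because everything else is meant to be the same in both arms. A rule that lets clinicians stop another drug in one arm only breaks that. Randomisation does not repair it, because the withdrawal follows allocation and depends on it. The result would then mix the effect of gaining dapagliflozin with the effect of losing something else.

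The mixture could mislead either way. Stopping a helpful drug in the study group could hide a real benefit. Stopping a drug that causes the outcome being counted could create an apparent one. Among the protocol's outcomes, blood pressure is exposed if an antihypertensive is the drug replaced, and hypoglycaemia if a glucose-lowering drug is.

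There is also a conduct problem. A clinician can follow a study-group-only rule only by knowing who is in the study group.

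**Working it through.** No figure in the plan is in dispute, so the check is to read the sections against each other and ask what each possible use of the option would estimate.

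**What the contrast becomes.** For one outcome, let:
- B = mean under placebo with full background treatment;
- D = effect of adding dapagliflozin, taken as the same whether or not another drug is stopped;
- f = fraction of the study group with a drug replaced;
- L = mean effect lost when that drug is stopped (either sign).

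One-arm rule, as written:
- study mean = B + D − f·L
- control mean = B
- difference = D − f·L

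Same rule in both arms:
- study mean = B + D − f·L
- control mean = B − f·L
- difference = D

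The protocol's Outcomes name D. The Technical design, if the option is used, delivers D − f·L. The two agree only if f or L is zero.

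**Four ways it could have played out.**
1. Never used: f = 0, and there is no bias and no threat to the blind.
2. Used in the study group only, after allocation: the difference is D − f·L, and someone had to know the assignment. This contradicts SAP section 2.
3. Applied to both arms at the start, by staff blind to assignment: the difference is D, but some placebo patients also lose a drug. Neither document says this was done.
4. Decided before randomisation and applied to both arms: the difference is D and the blind is intact. Neither document says this either.

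**Can the documents tell these apart, or bound f·L?** They cannot.
- L is not given for any drug.
- f is not given. The data to be collected, listed in the protocol, include no record of concomitant-drug changes.
- SAP Table 2 counts patients on ACE inhibitors or ARBs (27 of 38 study, 26 of 41 control) but does not say when the count was taken. Taken before any replacement, 27 would be the most who could lose such a drug; taken afterwards, it would be the number who kept one. It therefore gives no ceiling on f.
- SAP Table 1 shows 11 of 38 study patients with diabetes, but Table 2 lists no glucose-lowering drug, so the documents do not show that any of them had one to replace.
- SAP Table 10 reports increased steroid dose (7 control, 4 study) and intolerance of mycophenolate (1 control, 2 study). These bear on background treatment but do not show replacement by the study drug. The table has no hypoglycaemia row.

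The form of the bias is therefore known, but its size and direction are not.

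**The case against.** The strongest reply is that the SAP has overtaken the protocol sentence. That sentence also offers 10 mg and 25 mg; the SAP keeps only 10 mg, says nothing of replacement, and describes all staff as blinded. This is reasonable evidence that no one-arm swap took place. It stands as a reason not to assume bias. It does not settle the matter, because SAP section 2 is silent on background drugs and does not withdraw the option.

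Second, the control bullet is one short sentence and does not forbid replacement under placebo, so the asymmetry is partly read from silence. That is fair. But the option is written under the study group alone, and nothing extends it to controls.

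Third, the Research question and the Objectives can be read as asking about a treatment strategy, namely SGLT2 inhibition used as the clinician sees fit against usual care. ITT is valid for that question. This also stands, but the strategy is not specified: no drug, criterion or timing is given. It does not match the placebo contrast in the Outcomes or the SAP design.

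Two stronger readings are tempting. A reader might infer that the trial's results are biased or its blind was broken; no document shows that the option was used. A reader might instead infer that the point is harmless because Table 6 prints P = 0.9 for 12-month eGFR. That value is not safe support. With the printed means and SDs, and assuming 38 and 41 patients as in the other tables, SE = √(48²/38 + 44.5²/41) = 10.44 and the difference is 115.7 − 100.3 = 15.4. So z = 15.4/10.44 = 1.48, p about 0.14. That is still not significant, but it is not 0.9. A null result would not show the contrast was clean in any case, since losing a useful drug can mask benefit.

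**Conclusion.** The concern holds in conditional form. The protocol permits replacement of an unnamed drug in the study group only. If that was done as written, the trial did not estimate the dapagliflozin-versus-placebo effect that its Outcomes name, and the double-blind description would need qualifying. If it was never done, the results are unaffected and only the wording is at fault.

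I put no number on the bias. Any figure would rest on an assumed fraction replaced and an assumed loss per patient, neither of which the documents supply or bound. Severity is minor to moderate: the ambiguity concerns what was compared, it is cheap to resolve, and there is no sign that the option was exercised. The conclusion rests on reading the study-group bullet as limited to that group, and on the SAP's silence not amounting to withdrawal.

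**What to change.** For the protocol wording, and for any extension or repeat, choose one of two rules:
- dapagliflozin 10 mg or matching placebo is add-on only; or
- any replacement is decided and recorded before randomisation and applied identically in both arms.

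Align the Objectives and Research question with that one comparison. Which background rule is clinically right is for the investigators.

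The SAP gives the conduct dates as September 2022 to November 2023, so past conduct cannot be changed. For the completed trial, state in the report whether any drug was replaced. If none was, that one sentence closes the question about conduct. If some were:
- say which drugs, when, and on whose decision;
- tabulate background-drug changes by arm where clinic records allow, going beyond the steroid and mycophenolate rows in Table 10;
- keep ITT as the main analysis;
- describe the result as the effect of a treatment strategy;
- qualify the double-blind statement;
- say whether these patients count as major violations for the per-protocol set.

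The cost is slightly less prescribing freedom in future use and, for this trial, one sentence and at most one extra table. The table may be incomplete, because the protocol's data list has no concomitant-medication record.
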